2.0 INTRODUCTION

Relapse is an unfortunate event post-orthodontic treatment. Around 70% of patients post-orthodontic treatment are subjected to relapse (1,2). Patients usually talk about retention in a negative light in social media(3), where the main themes expressed included compliance, impact, maintenance, patient-clinician relationship, and positive and negative feelings. It is therefore important to ensure that the retention regime is effective and convenient for the patient.

Arch expansion is a common modality of treatment in correcting posterior crossbites. Methods of expansion often used in removable/fixed appliances would include archwire expansion, quadhelix, rapid maxillary expansion or removable appliances with a midline screw. Surgical methods have also been described (SARPE- Surgical Assisted Rapid Palatal Expansion) for severe cases. Expansion of the arches is considered very unstable and prone to 40% of relapse, regardless of any type of expansion, and this is mostly due to post-treatment growth pattern of the patient (4,5).

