5.0 METHODOLOGY

5.1 Participants Sampling

The sample will be selected from patients attending for orthodontic debond appointments at the Orthodontic Unit of Universiti Kebangsaan Malaysia (UKM), Klinik Pakar Ortodontik Klinik Kesihatan Bandar Botanik and Unit Pakar Ortodontik Klinik Pergigian Sungai Chua patients. The present practice at all 3 locations constructs Hawley and normal VFR retainers for all orthodontic patients. There are technicians and laboratory facilities to construct normal VFR as well as Hawley retainer. The only difference between modified and normal vacuum formed retainer is the outline of the retainers where the technician would trim the retainer, where it would cover the hard palate. Therefore it is only the location of trimming that is different using the same special trimming appliances for normal VFRs. Clinicians from KKM involved would be [name] [name] and [name] [name]. A screening will be done to select patients who are suitable of the study. Only patients who fulfil the criteria will be invited to participate in this study. Participant will be approached in the dental chair once deemed suitable, and will be given 5-10 minutes to decide on participation of the study. Consent will be gathered from the patients or the carer if the patient is below 18 years of age. The patients will then be randomly allocated into two groups using a randomized number computer generator, either the Hawley or the modified vacuumed formed retainers. The expected sample size to be of statistical significance will be calculated using the formula of sample size calculation relevant to this study. The sample size

calculation is based on a significance level of 0.05 and 80 percent power to detect a clinically meaningful difference of 2.0mm (SD=2.0mm) between the two groups in terms of arch width differences, where this difference are based on previous studies by Tynelius et al. (9) and Shawesh et al. (15). The power analysis gave a total sample size of 16 patients in each group. To account for attrition, 24 patients will be recruited in each group

The inclusion criteria of the subjects that will be included in the study are:

- a. Patients who are at least 13 years old at time of debond.
- b. Treatment plan of extraction or non-extraction followed by straight wire appliances in the upper arch only or both arches

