- c. Undergone expansion treatment in the upper arch causing an arch width increase of 3-10mm, either using a Quadhelix, Rapid Maxillary Expansion, expansion with archwires, or URA with midline screw. Patients' interarch measurements at the time of debond will be compared with their interarch measurements using the pre-treatment model available at the clinic.
- d. No chronic medical conditions

The criteria for suspending or terminating the study are:

- a. Relapse due to compliance issue
- b. Relapse due to investigative product
- c. Subject did not come for follow-up

The subject withdrawal criteria are:

- a. Voluntary

If relapse is found and/or if subjects request to withdraw from the study, subjects will be informed that they will not need to take impressions at follow-up but they still can make appointment with their orthodontist for a normal retainer review. If insignificant relapse is found, new Hawley retainers will be provided free of charge. If significant relapse is found in subjects from intervention group, free treatment will be provided. The withdrawn subjects will not be replaced and an Intention to Treat analysis (ITT) will be done.

The generation of randomization sequence will be performed in blocks of 12 to ensure that equal number of patients was allocated to each of the two retention groups. A randomized generator will be used for allocation. In this multi-centre trial, a centralized randomization technique which incorporated external involvement is used. Individuals who recruit subjects from each centre will contact a central methods centre by phone after patient enrolled in order to prevent selection bias and protect the assignment sequence until allocation. Calibrated researcher will collect the study models which the ID and intervention are covered by opaque tape once they are ready for measurement. Only one dental cast at a time will be picked out of its box without showing any previous measurements. Two dental casts from the same patient will not be measured in connection with each other. Due to the prospective nature of the study, it was inconvenient to anonymize dental casts from the start of the study.

Hawley retainer
(coverage)

Normal VFR retainer

Modified VFR (palatal

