5.4 Data management and analysis

Intra-examiner reliability of the measurements will be undertaken on two occasions in a random order and following an interval of two weeks.

A normality test will be conducted to determine whether a parametric or non-parametric test should be conducted. The outcome measures assessed will be the differences in means between groups, which will be assessed by one-way analysis of variance, using Statistical Package for Social Sciences (SPSS) version 17.0.

[4] -- Monday, July 08, 2019 -- 15:58:42

F tests - ANOVA: Repeated measures, between factors

Analysis: A priori: Compute required sample size

Input: Effect size f	=	0.42
α err prob	=	0.05
Power (1-β err prob)	=	0.80
Number of groups	=	2
Number of measurements	=	3
Corr among rep measures	=	0.5
Output: Noncentrality parameter λ	=	8.4672000
Critical F	=	4.1708768
Numerator df	=	1.0000000
Denominator df	=	30.0000000
Total sample size	=	32
Actual power	=	0.8038973

A reliability test will also be performed to calibrate the measurements made. The data will be reported in a collective manner with no reference to the specific individual. Publication policy by most journals would require removal of any personal details of any patient in any part of the article or in any supplementary materials (including all illustrations and videos) prior to submission, therefore the personal information from each individual will remain confidential. Access to the data is only by the research team (which involves orthodontists, dentists, personnel) and the REC UKM and KKM. The hard copy of the data obtained will be stored in a locked cupboard in a private room that could only be accessed by the research team. Soft copy of the data will be contained in a USB protection lock which password is only known to the research team. Data will be allowed for inspection or auditing by regulatory authorities. Data could be stored for at least 7 years before being destroyed (shredded) or deleted (electronic copy). Individuals have a right to know the results of their study and can contact the researchers if interested.

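### Age is used in neither the allocation nor the group comparison, although the plan ties expansion relapse to growth and enrols from 13 upward; adjusting for it would be a cheap gain in efficiency, not the repair of a bias

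*Combined protocol and SAP*

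**What the plan says.** - **Cause of relapse.** Section 2.0 describes expansion as unstable whatever the method used, and adds that "this is mostly due to post-treatment growth pattern of the patient". The Executive Summary (1.0) also links relapse in general to the passage of time and to age.
- **Who is enrolled.** Inclusion criterion a in section 5.1 reads "Patients who are at least 13 years old at time of debond". No upper age is given. The same section foresees minors and adults: "Consent will be gathered from the patients or the carer if the patient is below 18 years of age".
- **Allocation.** Section 5.1: "The generation of randomization sequence will be performed in blocks of 12 to ensure that equal number of patients was allocated". No stratification by age is stated.
- **Analysis.** Section 5.4 plans "differences in means between groups, which will be assessed by one-way analysis of variance", with a normality test deciding between parametric and non-parametric methods. No covariate is named anywhere.
- **Size.** Section 5.1: "calculation is based on a significance level of 0.05 and 80 percent power to detect a clinically meaningful difference of 2.0mm (SD=2.0mm"), then "The power analysis gave a total sample size of 16 patients in each group" and "To account for attrition, 24 patients will be recruited in each group".

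Age has to be known for the eligibility check and to decide who signs consent. No section lists it as a study data item or a baseline variable.

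**The concern.** The plan names a patient characteristic as the main cause of the outcome it measures, admits the whole range of that characteristic from 13 years upward, and uses no proxy for it in allocation or analysis. Two things are at stake in a trial of this size. Outcome variation that age could explain stays in the error term and widens the interval for the retainer difference. A chance difference in age between the arms also passes straight into the estimate.

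This matters more than usual because section 1.0 expects no difference between the retainers, and section 5.3 lets modified-retainer subjects who hear nothing continue with their retainer on the footing that it performs as well. A wide interval, or an estimate moved by imbalance, could be taken as reassurance.

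**Working it through.** **Inputs from the plan.** Difference 2.0 mm, SD 2.0 mm, alpha 0.05 (taken as two-sided, since the plan does not say), power 80%, 16 per arm required and 24 recruited (section 5.1).

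**Assumed inputs.** R², the share of outcome variance explained by age, is not in the documents; I show 0 to 30%. For the imbalance calculation I assume that half the subjects are under 18.

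**1. The plan's own figures.** By the normal approximation, n per arm = 2 × (1.960 + 0.842)² × 2.0² / 2.0² = 15.7, so 16. This reproduces. The t-test gives power 0.781 at 16 per arm and 0.924 at 24. The software output in section 5.4 also reproduces: λ = 0.42² × 32 × 3 / (1 + 2 × 0.5) = 8.467, power 0.804. That output is for a repeated-measures design with a different effect size, which is a separate matter and does not affect what follows.

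**2. Power with age in the model.** The residual SD is 2.0 × √(1 − R²). One degree of freedom is lost (error df = 2n − 3), and the variance of the group difference is multiplied by 1 + 1/(2n − 5) for expected chance imbalance in the covariate. Power is from the noncentral t with noncentrality (2.0/2.0) × √(n/2) / √[(1 − R²)(1 + 1/(2n − 5))].

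| R² | Power, 16 per arm | 95% CI half-width, 16 per arm | Power, 24 per arm |
|---|---|---|---|
| unadjusted | 0.781 | 1.44 mm | 0.924 |
| 0 | 0.766 | 1.47 mm | 0.918 |
| 0.04 | 0.782 | 1.44 mm | 0.928 |
| 0.10 | 0.808 | 1.40 mm | 0.942 |
| 0.20 | 0.851 | 1.32 mm | 0.963 |
| 0.30 | 0.894 | 1.23 mm | 0.980 |

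Break-even at 16 per arm is at about R² = 0.04 (a correlation of about 0.2). Over 10-30%, the gain is 3 to 11 points at 16 per arm and 2 to 6 points at 24. If age explains nothing, the loss at 16 per arm is 0.781 − 0.766, about 1.6 points before rounding. Scaling the SD alone, without the lost degree of freedom and the imbalance penalty, would give 0.822-0.905 at 16 per arm, which is too favourable.

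**3. How likely is an imbalance?** With half the subjects under 18 and independent binomial counts in each arm, the probability that the under-18 proportions differ by 25 points or more is 0.215 at 16 per arm and 0.111 at 24. If exactly half of those enrolled are under 18, the figures are 0.289 and 0.148.

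**4. What would it do to the estimate?** With a 50:50 split, an under-18 versus adult gap g explains R² = g² / (4 × SD²), so g = 2 × 2.0 × √R². For R² = 0.10, g = 1.26 mm; for R² = 0.30, g = 2.19 mm. A 25-point imbalance shifts the unadjusted estimate by 0.25 × g:

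- R² = 0.10: 0.25 × 1.26 = 0.32 mm
- R² = 0.30: 0.25 × 2.19 = 0.55 mm

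Against the 2.0 mm target this is 16% to 27%. To produce 2.0 mm from age alone at R² = 0.30, the imbalance would have to be 2.0 / 2.19 = 91 points. At R² = 0.10 even complete separation (1.26 mm) would not reach it.

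**The case against.** The strongest reply is that nothing here is invalid. Randomisation makes the unadjusted comparison unbiased on average and keeps the type I error. **This stands**, and it limits the point to efficiency and to the accuracy of the one estimate actually obtained.

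A reader might infer more, in four ways that the documents do not support:

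- *That age imbalance could mimic or hide the target effect.* On these assumptions the shift is about 0.3-0.55 mm, well short of 2.0 mm and inside the unadjusted half-width of 1.44 mm at 16 per arm.
- *That the plan itself calls growth its largest source of noise.* Section 2.0 makes a background statement about why relapse happens. It says nothing about the share of between-subject variance in width change over 12 months, and it names growth pattern, for which age is only a proxy.
- *That precision is certainly lost.* This depends on an R² that the documents do not give. Below about 4% adjustment gains nothing, and at the 24 per arm recruited unadjusted power is already 0.92.
- *That age is already recorded as trial data.* It is needed for eligibility and consent; its collection as a study variable is an inference.

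It can also be said that amount of expansion, type of expansion appliance and centre are equally plausible covariates. That is fair. The case for age is that the plan's own text points to it. Lastly, a one-way ANOVA takes no covariate, so the named test has to change. This is correct and belongs in the cost.

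**Conclusion.** The point holds as a recommended improvement in efficiency, not as a fault that invalidates the comparison. The plan gives a reason to expect age to be prognostic, enrols a wide age range in a small trial, and uses age nowhere. Of the sizes worked out above, the more relevant power gain depends on how many of the 24 per arm remain for analysis: it is modest if nearly all do, and more useful if attrition takes the arms down towards 16. The exchange is favourable, because the worst loss is smaller than the gain at the low end of the assumed range. The conclusion rests on the assumed R² of 10-30%, on half the subjects being under 18 for the imbalance figures, on a two-sided 0.05 test, and on age being a reasonable proxy for growth.

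**What to change.** In section 5.4:

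1. List age at debond as a data item to be recorded for every subject.
2. Replace the one-way ANOVA for the group comparison with an ANCOVA that pre-specifies age at debond as a covariate. Fix its form in advance: continuous in years, or an under-18 indicator. The indicator may suit better if growth is taken to stop in adulthood, since a straight line over an open adult range could fit poorly.
3. Report mean age and the number under 18 by arm. Do not select covariates by testing baseline differences.
4. State how the normality-test branch is to work under this model, because a covariate has no obvious place in a simple non-parametric test.

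**Cost.** A change of the named test, one degree of freedom, and at worst about 1.6 points of power at 16 per arm. No extra visits or measurements are needed.

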5.4.1 Dental casts

Dental casts of four occasions will be obtained, on the day of removal of orthodontic appliances (T0), 3 months post- removal of orthodontic appliances (T1), 6 months post-removal of orthodontic appliances (T2) and 12 months post-removal of orthodontic appliances (T3). Based on a previous study (9), linear measurements will be made with an electronic digital calliper on the dental cusps to a precision of 0.01mm:

- Intercanine width in the maxilla- the distance between the canine cusp tips
- Interpremolar width in the maxilla- the distance between the premolar cusp tips
- Intermolar width in the maxilla- the distance between the mesiobuccal cusp tips of the first molars

Landmarks of cusp tips are identified based on guidelines described in the literature, where the most prominent tip is selected (9). If attrition is present, the centre of the surface area is determined to be the point of measure.

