A number of subjects who fulfil the criteria will be invited to participate in this study. The study will involve arch width analysis using study models pre, post-debond, 3 months review post-debond, 6 months review post-debond and 12 months review post-debond. All data will be analyses using Statistical Package for Social Sciences (SPSS). The arch width of subjects post-fixed appliances will be compared. Most studies compare the arch width, as well as lower incisor irregularity in evaluating relapse in different groups of retainers. However, there are currently no randomized control trials comparing expansion cases of Hawley vs vacuum formed retainers, hence why this study will be conducted.

We expect to see no difference between the modified vacuum formed retainer and Hawley retainer in terms of maintaining arch expansion post-orthodontic treatment. This would therefore mean that there would be a simpler method and would be a suitable more cost-effective alternative as compared to constructing Hawley retainers or adding a palatal wire on the vacuum formed retainers.

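### Expansion gained before entry (3 to 10 mm) has no stated role in the analysis, although the pre-treatment model is already to hand; adjusting for it would give a modest gain in precision and a clearer reading of the result

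*Combined protocol and SAP*

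**What the plan says.** Section 5.1 admits patients whose upper arch width rose by 3 to 10 mm. It checks this against existing records: "Patients' interarch measurements at the time of debond will be compared with their interarch measurements using the pre-treatment model available at the clinic". The T0 column of the monitoring table in section 5.2 words the rule as 3 mm, with no upper limit.

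The executive summary (section 1.0) includes the pre-treatment model among those analysed: "The study will involve arch width analysis using study models pre, post-debond, 3 months review post-debond, 6 months review post-debond and 12 months review post-debond". Section 5.2 (data analysis) and section 5.4.1 start at debond. The latter reads "Dental casts of four occasions will be obtained, on the day of removal of orthodontic appliances (T0", followed by 3, 6 and 12 months, with inter-canine, inter-premolar and inter-molar widths read by calliper.

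Section 5.4 compares group means by one-way ANOVA and names no covariate. Section 5.1 describes blocked allocation without stratification by expansion. The sample size is set to "detect a clinically meaningful difference of 2.0mm (SD=2.0mm) between the two groups". The introduction says of relapse: "Expansion of the arches is considered very unstable and prone to 40% of relapse".

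**The concern.** The hypothesis in section 3.0 is about relapse of arch expansion, so the amount of expansion is the natural baseline quantity. It may vary more than threefold between patients (10/3 = 3.3). T0 width does not stand in for it, because two patients with the same T0 width may have gained 3 mm and 10 mm.

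If relapse depends on the amount gained, leaving it out of the model puts explainable variation into the error term of a small trial. A mean difference in mm also has no fixed meaning across such a population. This matters because the investigators expect to find no difference, and section 5.3 lets patients who are not contacted take it that their modified retainer is adequate. A result of that kind should be as precise and as readable as the available data allow.

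**Working it through.** **Inputs from the documents.** Difference 2.0 mm, SD 2.0 mm, alpha 0.05, power 0.80, 16 per group needed, 24 per group recruited, expansion 3 to 10 mm (all section 5.1). Alpha is taken as two-sided because the hypothesis is one of a difference.

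**Step 1: the plan's own figure.** n per group = 2 × (1.960 + 0.842)² × 2.0² / 2.0² = 15.7, so 16. This reproduces. The section 5.4 printout also reproduces: λ = 0.42² × 32 × 3 / (1 + 2 × 0.5) = 8.467, with power 0.804. With the exact t distribution, a 2.0 mm difference at SD 2.0 mm has power 0.78 at 16 per group and 0.92 at 24.

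**Step 2: what 2.0 mm means across the entry range (no assumption needed).** 2.0/3 = 67% of the smallest permitted correction; 2.0/10 = 20% of the largest.

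**Step 3: possible gain from adjustment.** Two inputs are not in the documents and are assumed:
- Gains are uniform over 3 to 10 mm, so their SD is 7/√12 = 2.02 mm.
- Relapse rises linearly with expansion gained, with slope b. The value b = 0.4 is what results if the introduction's 40% is read as the share of expansion lost. Smaller slopes show how far the answer depends on that reading.

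The planning SD of 2.0 mm is taken to include this source of variation. Then:
- SD of relapse due to expansion = b × 2.02
- share of variance = (b × 2.02 / 2.0)²
- residual SD = 2.0 × √(1 − share)
- 95% range of the chance shift in the unadjusted difference = ±1.96 × b × 2.02 × √(2/n)

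| Slope b | SD from expansion (mm) | Share of variance | Residual SD (mm) | Shift, 16 per arm (mm) | Shift, 24 per arm (mm) | Power, 16 per arm |
|---|---|---|---|---|---|---|
| none (unadjusted) | – | – | 2.00 | – | – | 0.78 |
| 0.1 | 0.20 | 1% | 1.99 | ±0.14 | ±0.11 | 0.79 |
| 0.2 | 0.40 | 4% | 1.96 | ±0.28 | ±0.23 | 0.80 |
| 0.4 | 0.81 | 16% | 1.83 | ±0.56 | ±0.46 | 0.85 |

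The power figures ignore the one degree of freedom spent on the covariate, which costs about 0.001.

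**Step 4: the same gain as interval width.** At 16 per arm, the 95% half-width is 1.96 × 2.0 × √(2/16) = 1.39 mm unadjusted. At b = 0.4 it is 1.96 × 1.83 × √(2/16) = 1.27 mm adjusted. At 24 per arm and b = 0.4, power goes from 0.92 to 0.96.

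**The case against.** The strongest reply is that this is a covariate preference and not an error. Much of that stands, and it rules out several stronger readings that a reader might infer.

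- *The pre-treatment width has been dropped.* Section 5.4.1 lists casts still to be obtained. The pre-treatment model already exists, so its absence from that list is no proof of exclusion, and the executive summary includes it. The sections are incomplete or inconsistent; no more can be said.
- *The trial is biased or underpowered by this.* Randomisation keeps the unadjusted comparison unbiased on average. The chance shifts above are not an extra error if the SD of 2.0 mm already contains them, because the standard error then does too.
- *Expansion gained is a known driver of relapse.* No section says so. The introduction attributes relapse mostly to post-treatment growth.
- *The plan itself puts relapse at 40% of the expansion.* The wording could mean a share of patients; the same section gives a patient incidence of about 70% for relapse after orthodontic treatment in general. It states neither a follow-up time nor a retention regime. The slope of 0.4 is therefore an assumption.
- *Differences under 2.0 mm will be dismissed.* The 2.0 mm is a planning difference between group means. Although it is called clinically meaningful, no rule declares smaller differences unimportant or classifies an individual loss.

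It is also fair to say that the plan never states whether width, change in width or percentage is compared. The mm scale is inferred from the calliper readings and the sample-size statement. That gap is wider than this point, but the fix below closes it for this comparison.

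What the reply does not answer is that a relevant baseline value is available for every entrant, is mentioned in the summary, and has no use in the methods.

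**Conclusion.** The point holds as a modest, inexpensive improvement in precision and interpretation. It does not challenge the validity of the comparison or the sample size. The contrast of 67% with 20% rests on the documents alone. The precision gain does not: under uniform gains it runs from negligible (1% of variance at slope 0.1) to useful (16% at slope 0.4, with power at 16 per arm rising from about 0.78 to 0.85). The documents cannot show where in that range the truth lies. The executive summary and sections 5.2 and 5.4.1 need to be reconciled whatever the slope.

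**What to change.** Before outcome data are seen:

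1. Add the existing pre-treatment cast to section 5.4.1, and align sections 1.0, 5.2 and 5.4.1. Have it read blinded, at the same landmarks as the other casts. The screening comparison may not suffice, since section 5.1 does not say which width the 3 to 10 mm refers to.
2. State the outcome as width loss from T0 in mm, at each named width.
3. Replace the one-way ANOVA with an ANCOVA on retainer group, with expansion gained at that width (T0 minus pre-treatment) as a prespecified covariate.
4. Report loss as a share of expansion gained only as a supporting summary. It should not be the endpoint, because the ratio is unstable where little expansion occurred.

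The cost is one degree of freedom and a set of extra calliper readings, with no new visit or impression. Two drawbacks should be acknowledged. The covariate shares T0 measurement error with the outcome. In extraction cases, which are eligible, the plan must name the same premolar before and after treatment.
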